Additionally, in the CLIK066B2201 dose finding study in obese or overweight adults in North America and Europe to evaluate weight loss after 24 weeks, 460 participants were randomized to either placebo, QD doses ranging from 2.5 to 150 mg, or BID doses ranging from 2.5 to 50 mg. After 24 weeks of treatment, there was a dose dependent reduction in body weight, with change from baseline of -3.6% in the 50 mg qd group and -4.6% in the 150 mg QD group. In the CLIK066B1201 dose finding study to evaluate weight loss after 12 weeks in Japanese obese participants, 126 participants were randomized to either placebo or doses ranging from 2.5 to

50 mg QD. After 12 weeks, there was a dose dependent reduction in body weight, with change from baseline of -3.41% in the 25 mg group and -3.80% in the 50 mg group.

CLIK066X2204 study tested licogliflozin at doses of 30 and 150 mg for 12 weeks in NASH participants. Results from full study population confirmed that treatment with licogliflozin at 150 mg and 30 mg per day resulted in dose-dependent improvements in markers of liver injury (ALT, AST and GGT) and liver fat content. (LIK066 IB Edition 12) The study clinical report is currently in preparation. Both doses of licogliflozin led to significant placebo adjusted weight loss at the 150 mg and 30 mg doses respectively (LIK066 IB). Licogliflozin treatment also improved glycemic and insulin sensitivity markers; HbA1c and HOMA-IR at both doses. The most common AE was diarrhea, reported by similar number of participants in the placebo and 30 mg groups but at a higher rate in the 150 mg dose group. As in previous studies with licogliflozin, diarrhea was mostly mild in the participants who had it. Only one participant in the 150 mg dose group discontinued treatment as a result of diarrhea.

In summary, in clinical studies, licogliflozin has been well tolerated to date, resulting in improvements in markers of liver injury, hepatic fat, and weight loss with doses tested up to 150 mg orally in the CLIK066X2204 study.

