1.2 Purpose

The purpose of this study is to compare tropifexor and licogliflozin in combination therapy and each monotherapy to placebo for efficacy, safety, and tolerability in participants with NASH and liver fibrosis (stage 2 or 3) as per NASH clinical research network (CRN) histological score.

2 Objectives, endpoints and estimands

Objective(s)	Endpoint(s)		
Primary objective(s)	Endpoint(s) for primary objective(s)		
• To evaluate the efficacy of tropifexor + licogliflozin in combination therapy and each monotherapy treatment, as assessed by histologic improvement after 48 weeks compared to placebo in participants with NASH and stage 2 or 3 fibrosis.	 Whether the participant achieves at least one stage of improvement in fibrosis without worsening of NASH at Week 48 compared to Baseline Whether the participant has resolution of NASH without worsening of fibrosis at Week 48 compared to Baseline 		
Secondary objective(s)	Endpoint(s) for secondary objective(s)		
• To evaluate the efficacy of combination therapy and two monotherapies in NASH or fibrosis with a composite endpoint after 48 weeks of treatment.	• Key secondary endpoint: Whether the participant achieves resolution of NASH and no worsening of fibrosis OR improvement in fibrosis by at least one stage without worsening of NASH at Week 48 compared with Baseline.		
 To evaluate improvement in fibrosis by at least one stage after 48 weeks of treatment. 	 Whether the participant has at least one stage improvement in fibrosis at Week 48 compared with Baseline 		
• To evaluate improvement in fibrosis by at least two stages with no worsening of NASH after 48 weeks of treatment	 Whether the participant has at least two stage improvement in fibrosis without worsening of NASH at Week 48 compared with Baseline 		
 To evaluate reduction in body weight from Baseline after 48 weeks of treatment 	• Whether the participant has 5% or more reduction in body weight at Week 48 compared to Baseline		
• To evaluate change in liver fat content after 48 weeks of treatment	 Change in liver fat content based on MRI - PDFF (in 40% of participants) over time up to Week 48 compared with Baseline 		

Table 2-1Objectives and related endpoints

NovartisConfidentialPage 62 of 160Amended Protocol Version 02 (Clean)Protocol No. CLJN452D12201C

Amended Protocol Version 02 (Clean)	Protocol No. CLJN452D12201C
Objective(s)	Endpoint(s)

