12.5.1 Efficacy

endpoint(s)

Secondary efficacy endpoints will be analyzed in the FAS and planned analyses are outlined in Table 12-1 below:

Novartis ---- Confidential

Table 12-1Planned Analyses	
Endpoints	Analysis
Key secondary endpoint: whether the participant achieves resolution of NASH and no worsening of fibrosis OR Improvement in fibrosis by at least one stage without worsening of NASH at Week 48 compared with baseline.	Same statistical methods as for one branch of the primary analysis with overall Type I error rate controlled at two sided 0.05 level.
Whether (yes or no) the participant has at least one stage improvement in fibrosis at week 48 compared with baseline	Same statistical methods as for the key secondary endpoint analysis with neither hypothesis tests nor p-values.
Whether (yes or no) the participant has at least two stage improvement in fibrosis stage and no worsening of NASH at week 48 compared with baseline	Same statistical methods as for the primary analysis with neither hypothesis tests nor p-values.
Change in liver fat content based on MRI - PDFF (in 40% of participants) over time up to Week 48 compared with baseline	Descriptive statistics, adjusted mean and mean differences of treatment of interest vs. alternative treatment with 95% CI by scheduled visits based on repeated measurement analysis of covariance (ANCOVA) model will be presented.
Whether (yes or no) the participant has 5% or more reduction in body weight at Week 48 compared to baseline	Number and percentage of participants with 5% or more reduction in body weight. Difference in percentages between treatment of interest and alternative treatment along with 95% CI calculated based asymptotic normal distribution of difference in proportions will be presented. CMH test stratified with baseline T2DM status will be performed to estimate odds ratio (95% CI) between treatment of interest and alternative treatment.
Change in ALT and AST over time up to Week 48 compared with Baseline	The mixed model of repeated measurement will be fitted to changes from baseline in these endpoints over time. The point estimate and the associated 95% CI of the change from each treatment at each visit will be presented.
Change in GGT over time up to Week 48 compared with Baseline	The mixed model of repeated measurement will be fitted to changes from baseline in GGT over time. The point estimate and the associated 95% CI of the change from each treatment at each visit will be presented.

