12.5.2.3 Vital signs

The change from baseline in vital sign parameters, including Anthropometric measurements, will be summarized at scheduled post-baseline visits by treatment group. Change from baseline will only be summarized for participants with both baseline and post-baseline values.

[figure not shown]
Participants with clinically notable vital signs as defined in Section 16.1 will be listed.

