# 2.7.2 Statistical hypothesis, model, and method of analysis

There is no hypothesis test planned for these additional secondary endpoints.

Binary histologic endpoints will be analyzed using the same logistic regression model for primary endpoint following an ITT approach (Section 2.5.4). The number (%) of responders will be summarized by study treatment. The difference between the combination therapy and each monotherapy will be presented along with Wald asymptotic 95% CI. The Odds Ratios (with 95% CI) between combination and each monotherapy estimated from the logistic regression model will also be provided.

Repeated measurements ANCOVA models for the change in liver fat fraction will include time (visit) and treatment group as categorical explanatory variables, with interaction between treatment and visit also included in the model. More details of the model are discussed in Section 5.4.3. The analysis may be implemented with SAS MIXED procedure, assuming an unstructured variance-covariance matrix for repeated measurements and using Kenward-Rogers type degrees of freedom. Estimates of the differences (95% CI) between treatment groups may be obtained using the LSMEANS and ESTIMATE statements in the SAS procedure at individual time points. Descriptive statistics, adjusted mean and adjusted mean differences (95% CI) between combination and monotherapies will be presented by visit.

For proportion of patients with at least 5% reduction of body weight at week 48, the number (%) of patients will be summarized by study treatment. Difference in percentages will be presented with Wald asymptotic 95% CI. A CMH analysis stratified by baseline T2DM status will be performed to estimate the common odds ratio (95% CI) between combination and each monotherapy. CMH analysis may be implemented with the SAS FREQ procedure following similar implementation in the sensitivity analysis on primary endpoint (Section 5.4.4) but with only baseline T2DM status as stratification factor.

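### The body-weight objective is compared between arms only as a yes/no 5% cut; adding a repeated-measures analysis of percent weight change would recover lost precision at the cost of one table

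*Protocol*

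**What the plan says.** Protocol Table 2-1 states the objective on the measured scale: "To evaluate reduction in body weight from Baseline after 48 weeks of treatment". The only endpoint attached to it is binary: "Whether the participant has 5% or more reduction in body weight at Week 48 compared to Baseline".

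Protocol Table 12-1 gives the analysis: "Number and percentage of participants with 5% or more reduction in body weight", then "Difference in percentages between treatment of interest and alternative treatment along with 95% CI", and finally "CMH test stratified with baseline T2DM status will be performed to estimate odds ratio (95% CI) between treatment of interest and alternative treatment". SAP 2.7.2 matches this ("For proportion of patients with at least 5% reduction of body weight at week 48, the number (%) of patients will be summarized by study treatment") and adds a Wald interval for the difference and a CMH common odds ratio stratified by T2DM. It states that no hypothesis test is planned for these endpoints. SAP 2.7.3 fills a missing Week 48 weight with the last available value, which may be the baseline value.

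Weight is recorded to 0.1 kg (protocol 8.3.1.1) and scheduled at every visit (Table 8-1). The only other readable use of it is under safety. Protocol 12.5.2.3 says: "The change from baseline in vital sign parameters, including Anthropometric measurements, will be summarized at scheduled post-baseline visits by treatment group". SAP 2.8.4.2 lists body weight among the values summarised by visit and treatment, on the safety set, with no between-arm estimate.

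In the same Table 12-1, liver fat, measured in 40% of participants, gets a repeated-measures ANCOVA with adjusted mean differences and 95% CIs by visit.

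**The concern.** The objective asks how much weight is lost, and the planned comparison asks how many participants cross one line. A participant who loses 4.9% counts the same as one who gains weight, and the interim visits inform the comparison only by supplying a carried-forward value when Week 48 is missing.

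The question matters for interpreting the trial. Protocol 4.1 lists weight loss first among licogliflozin's expected contributions, 4.5.2.1 links weight loss to histologic improvement, and 4.2 uses the dose-weight curve to support 30 mg. Protocol 1.1.3 reports weight reduction with tropifexor as well, so whether the combination exceeds each single drug is a genuine question. An interval wider than the data require could leave a real difference of a few percent looking inconclusive.

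**Working it through.** **Stated figure.** The documents give no power for body weight. The nearest figure is Table 12-5: 0.85 for at least one combination-versus-placebo histology test at 140 vs 80. Simulating the two endpoints (35% vs 20%, 25% vs 10%, correlation 0.5, two-sided 2.5% each) with an unpooled z-test gives 0.849, and about 0.80 at 95 vs 95 (stated 0.80). A pooled variance gives 0.798 at 140 vs 80 and does not reproduce the table. The unpooled form is also the interval that SAP 5.6.1 specifies, so it is used below.

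**Inputs from the documents.** Arm sizes are 140 and 80 (protocol 12.8.1). Protocol 4.5.2.1 gives a decrease of about 2-3% versus placebo for marketed SGLT2 inhibitors. For licogliflozin, protocol 1.1.4 reports a 12-week Japanese obesity study "with change from baseline of -3.41% in the 25 mg group and -3.80% in the 50 mg group", and -3.6% at 50 mg once daily in a 24-week study. These are changes from baseline, not placebo-adjusted.

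**Assumed, because the documents do not give them.** Percent change is normal with SD 4-7 points; placebo mean is 0 to -2%; data are complete. The criterion is whether the two-sided 95% CI excludes no effect.

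**Formulas.** Responder rate: p = Φ((-5 - mean)/SD). For the cut: z = (p1 - p0)/√[p1(1-p1)/n1 + p0(1-p0)/n0], and the chance is about Φ(z - 1.96). For the mean: a two-sample t-test with noncentrality difference/[SD·√(1/n1 + 1/n0)].

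**Centre case: difference 2.5, SD 5, placebo mean -1%, active mean -3.5%.**
- Placebo rate: Φ(-4/5) = 0.212. Active rate: Φ(-1.5/5) = 0.382. Difference: 0.170.
- 80 vs 80, cut: SE = √(0.00295 + 0.00209) = 0.0710; z = 2.40; Φ(0.44) = 67%.
- 80 vs 80, mean: 2.5/(5 × 0.1581) = 3.16; 88%.
- 140 vs 80, cut: SE = √(0.00169 + 0.00209) = 0.0614; z = 2.77; Φ(0.81) = 79% by this approximation, 78% by enumerating the binomial outcomes.
- 140 vs 80, mean: 2.5/(5 × 0.1402) = 3.57; 94%.

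**Other cases (cut against mean).**

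| Case | 5% cut | Mean % change |
|---|---|---|
| 80 vs 80, difference 2.5, SD 6, placebo -1% | 53% | 75% |
| 140 vs 80, difference 2.5, SD 6, placebo -1% | 64% | 84% |
| 112 vs 64 (20% fewer), difference 2.5, SD 5, placebo -1% | 70% | 89% |
| Combination vs monotherapy, 140 vs 80, difference 1.5, SD 5, monotherapy -3% | 40% | 57% |
| 140 vs 80, difference 4, SD 5, placebo -1% | 99% | 100% |
| 140 vs 80, difference 4, SD 6, placebo -1% | 96-97% | 99.7% |

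Over differences of 2-3 points, SD 4-7 and placebo 0 to -2%, the loss is about 4 to 33 points at 80 vs 80 and 1 to 26 points at 140 vs 80. The small losses occur where both methods are already near certain.

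**The case against.** **The analysis fits its endpoint, and 5% is not arbitrary.** The responder endpoint is pre-specified and the analysis follows from it. The documents use a 5% weight change elsewhere (exclusion criterion 3), and SAP Table 5-4 cites an association between weight-loss categories and histology. This stands: it is a reason to keep the endpoint. It does not explain why a measured-scale comparison is absent, and the readable text gives no source for the 5% threshold.

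**The weights are reported.** By-visit change appears for each arm, so a reader could see the pattern. That is correct, but those summaries are descriptive, on the safety set, and carry no between-arm interval.

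**Redaction.** A reader might infer that no between-arm analysis of measured weight exists anywhere. The documents do not support that. Protocol numbering jumps from 12.5.2.4 to 12.7, and the readable SAP from 2.8.4.2 to 2.14, so an exploratory weight model could sit in a gap. It would still not be the stated analysis of the secondary objective.

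**The effect size is borrowed.** A reader might take 2-3% as the loss this protocol expects. It is a figure for marketed SGLT2 inhibitors, and the licogliflozin figures come from shorter obesity studies. Tropifexor may add weight loss, so the combination-placebo difference could exceed 3 points and the loss could then nearly vanish. This stands for that comparison. Comparisons with the monotherapies may involve smaller differences.

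**The contrast with other endpoints is limited.** The ALT, AST and GGT rows promise estimates for each treatment, not between-arm differences. Only liver fat is a true parallel.

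**Conclusion.** The point holds as one about precision. In the readable text, the body-weight objective has between-arm estimates only on the 5% cut, and weights collected at every visit are not otherwise used to compare arms.

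A reader might infer a fixed loss of 15 to 25 points of power. The documents do not support that statement: it needs an SD and a placebo change they do not give, and no test is planned here, so the figures describe how often a 95% CI would exclude no effect. With the planned unpooled interval, the centre case loses about 21-22 points at 80 vs 80 and 15-17 at 140 vs 80. Those values lie within the wide ranges shown above and rest on normality and complete data.

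Nor do the documents support replacing the responder endpoint. The case is for adding an analysis beside it. This is a cheap improvement, not a flaw that threatens the trial's conclusions.

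**What to change.** Keep the 5% responder endpoint, its difference in percentages and its CMH odds ratio as pre-specified. Add to protocol Table 12-1, and to SAP Table 2-5 and 2.7.2:

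- a repeated-measures model on the FAS for percent change from baseline in body weight over the scheduled visits to Week 48, with treatment, visit, treatment-by-visit, T2DM status and baseline weight;
- adjusted mean differences with 95% CIs for the same pairwise comparisons as the responder analysis, without p-values.

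The covariance structure and degrees of freedom in SAP 5.4.3, and the Group 1 visit windows in SAP Table 2-1, can be reused. The available SAP covers three arms and 210 patients, so its comparisons need updating to the four-arm protocol in any case.

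The cost is one extra table. No new data, visits or alpha are needed. The model assumes missing at random, whereas the responder analysis carries the last value forward, including baseline. The SAP should state that difference so that a divergence between the two results can be interpreted.

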• To evaluate the relationship of investigational treatment and markers of hepatic inflammation in NASH (ALT and AST) after 48 weeks of treatment	 Change in ALT and AST over time up to Week 48 compared with Baseline
• To evaluate the relationship of investigational treatment and GGT, a marker of cholestasis and oxidative stress after 48 weeks of treatment	Change in GGT over time up to Week 48 compared with Baseline
 To evaluate the safety and tolerability of tropifexor (LJN452) in combination with licogliflozin (LIK066), and each monotherapy treatment, compared to placebo, after 48 weeks of treatment 	 Occurrence of adverse events, serious adverse events, adverse events resulting in discontinuation of study treatment, adverse events of special interest and changes in vital signs and laboratory parameters

Novartis Amended Protocol Version 02 (Clean)	Confidential	Page 63 of 160 Protocol No. CLJN452D12201C

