#### 2.7.1 Secondary efficacy endpoints

Endpoint	Analysis
Proportion of patients who have at least one stage improvement in fibrosis at week 48 compared with baseline	Same analysis methods as for the primary endpoint following the ITT principle (Section 2.5.4 ) without hypothesis test.
Proportion of patients who have at least two stage improvement in fibrosis and no worsening of NASH (no worsening of hepatocellular ballooning or lobular inflammation) at week 48 compared with baseline	Same analysis methods as for the primary endpoint following the ITT principle (Section 2.5.4 ) without hypothesis test.
Change in liver fat content based on MRI - PDFF (in 60% of patients) over time up to Week 48 compared with baseline	Repeated measurement analysis of covariance (ANCOVA) model (Section 5.4.3) will be used to estimate treatment group differences in mean change from baseline and 95% CI. This analysis is on FAS patients with at least one MRI-PDFF assessment.
Proportion of patients with 5% or more reduction in body weight at Week 48 compared to baseline	CMH test stratified with baseline T2DM status will be performed to estimate odds ratio (95% CI) between combination arm and each monotherapy

 Table 2-5
 Secondary efficacy variables and methods of analysis

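### For ALT, AST and GGT, Protocol Table 12-1 pre-specifies each arm's own change but no difference between arms, so the effect versus placebo and its confidence interval are not a planned output

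*Protocol*

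**What the plan says.** Protocol Section 12.5.1, Table 12-1, has one row for ALT and AST and one for GGT. Each fits a mixed model for repeated measures to change from baseline; for GGT the text is "The mixed model of repeated measurement will be fitted to changes from baseline in GGT over time". Each row then closes with the same statement of output: "The point estimate and the associated 95% CI of the change from each treatment at each visit will be presented". Neither row mentions placebo, another arm or a difference.

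The other rows of Table 12-1 are comparative. The MRI-PDFF row asks for "adjusted mean and mean differences of treatment of interest vs. alternative treatment with 95% CI by scheduled visits". The body-weight row asks for "Difference in percentages between treatment of interest and alternative treatment along with 95% CI", together with an odds ratio. The key secondary composite uses the methods of one primary branch. The two remaining fibrosis rows take over the primary or key secondary methods, odds ratios included, without tests or p-values.

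The objectives in Protocol Table 2-1 read "To evaluate the relationship of investigational treatment and markers of hepatic inflammation in NASH (ALT and AST) after 48 weeks of treatment" and "To evaluate the relationship of investigational treatment and GGT, a marker of cholestasis and oxidative stress after 48 weeks of treatment". Neither names a comparator. The study purpose in Section 1.2 does: it is to "compare tropifexor and licogliflozin in combination therapy and each monotherapy to placebo for efficacy, safety, and tolerability".

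**The concern.** Change within an arm is not an effect of the drug. All arms receive diet and exercise counselling (Protocol 6.7.2.2), and insulin and lipid-lowering doses may be adjusted during the study (6.2.1, 10.2.3.2). Any of these could plausibly move liver enzymes in every arm. Section 8.3.2 treats sustained ALT improvement as a valid measure of efficacy, so readers will want the difference from placebo.

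If the plan does not name that difference, the choice of comparisons, visit and model terms is left open until after unblinding. Readers given only arm-level intervals may also fall back on asking whether the intervals overlap, or which ones exclude zero. The first is an inefficient comparison of arms and the second is not a comparison at all.

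**Working it through.** **Is the contrast specified anywhere else?**

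- Protocol 12.5 promises descriptive summaries by treatment group and visit for secondary endpoints. It gives no contrast.
- The Amendment 01 summary records that the repeated-measures description below Table 12-1 was removed because these analyses are now described in the table itself. Table 12-1 is therefore the protocol's operative specification.
- The SAP's Table 1-1 lists the ALT, AST and GGT objectives. Its Table 2-5, "Secondary efficacy variables and methods of analysis", has no row for them.
- SAP 2.7.2 describes between-arm differences from the repeated-measures model, but for liver fat fraction.
- SAP 2.1.1 sets visit windows for liver tests to support by-visit analysis on the full analysis set, but the text available does not say what that analysis reports. SAP 2.8.3 gives descriptive laboratory summaries on the safety set.
- The SAP is dated December 2019 and covers three arms without placebo, so it could not supply a placebo contrast in any case.

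**Is the contrast available from the planned model?** Yes. SAP 5.4.3 includes treatment among the fixed effects, and SAP Section 4, item 4.6, confirms a treatment-by-visit interaction. If the enzyme models follow this form, a difference at each visit is a linear contrast of parameters already estimated.

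**How much does a direct interval gain over reading separate ones?** The documents give no SD, effect size or power for ALT, AST or GGT, so there is no stated figure to reproduce. The illustration is in SD units. It assumes equal SDs, independent arm means and full planned arms: 140 on combination and 80 in each other arm (Protocol 6.1.3).

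Half-width of one arm's 95% interval, 1.96/√n:
- n = 80: 1.96/√80 = 0.219 SD
- n = 140: 1.96/√140 = 0.166 SD

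Half-width of the 95% interval for a difference, 1.96·√(1/n₁ + 1/n₀):
- 140 vs 80: 1.96 × 0.1402 = 0.275 SD
- 80 vs 80: 1.96 × 0.1581 = 0.310 SD

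Gap needed before two separate intervals stop overlapping (sum of the arm half-widths):
- 140 vs 80: 0.166 + 0.219 = 0.385 SD, and 0.385/0.275 = 1.40
- 80 vs 80: 0.219 + 0.219 = 0.438 SD, and 0.438/0.310 = 1.41

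Requiring non-overlap corresponds to a two-sided level of about 0.006 in both cases. Also, a placebo change just above 0.219 SD would give a placebo interval that excludes zero with no drug involved, so an interval excluding zero in an active arm does not by itself show a drug effect.

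**Sensitivity to missing data.** The protocol expects about 20% missing Week 48 biopsies (12.8.1). If the same share of enzyme values were missing, which is an assumption, the widths would grow by 1/√0.8 = 1.118, to about 0.307 and 0.347 SD. The 1.4 ratio would not change.

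**The case against.** A reader might infer that these endpoints cannot show a treatment effect, or that their objectives go unanswered. The documents do not support either reading. Placebo is a concurrent, randomised, double-blind arm, and its change and interval will stand beside those of the active arms. Counselling, concomitant medication and regression to the mean act on placebo too, and their effect would be visible there. Subtracting two arm estimates gives the effect, and an approximate interval follows from the two standard errors. Nothing in the plan says that arms will be judged by overlap or by which interval excludes zero. The objectives ask about a relationship between treatment and marker without naming a comparator, and arm-level estimates address that in part.

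Nor should one infer that placebo was added because enzyme changes are hard to interpret. The amendment rationale cites committee and authority advice and high placebo response rates, and Protocol 4.3 ties the concern to variability in histological response.

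The SAP's silence is weak evidence. It predates Amendment 01, which records adding the ALT, AST and GGT analyses to Table 12-1, and it says it may be amended when the protocol is. Some of its sections are not visible in the public copy.

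These points limit the concern but do not remove it. The rows that state the analysis name only within-arm output. The absence of a hypothesis test does not explain this, because the MRI-PDFF row names no test either and still reports differences with intervals. A reconstruction from published arm estimates is approximate, since estimates from one adjusted model need not be fully independent and the covariates for these rows are not stated.

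**Conclusion.** The point holds as a gap in pre-specified reporting. For ALT, AST and GGT the protocol commits to each arm's change with its interval, and does not commit to the difference from placebo or between active arms. In a trial whose stated purpose is comparison with placebo, that difference should be a planned output.

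The consequence is modest. No alpha, power or sample-size figure depends on these rows, no test is named for them, and the effect remains estimable. Without the contrast, a reader relying on non-overlap would need a gap about 1.4 times the half-width of the direct interval. The SD-unit widths rest on full arms, equal SDs and independent arm means; they show scale and do not predict precision. The change is worth making because it gives a better output from a model already planned.

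**What to change.** In the ALT/AST and GGT rows of Table 12-1, add the adjusted mean difference with 95% confidence interval at each visit, from the same repeated-measures model, for the five comparisons already listed in Protocol 12.4.2: combination and each monotherapy versus placebo, and combination versus each monotherapy. Name Week 48 as the main time point and state that no hypothesis test is performed, in line with the MRI-PDFF row. Keep each arm's change as a descriptive result.

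Carry the same text into the four-arm SAP update, with an ALT/AST row and a GGT row in the secondary efficacy table and the model terms stated (treatment, visit, their interaction and the covariates).

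The cost is a few lines of text and additional contrast output. No new data, participants or alpha are needed.
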